HRQoL	Health-Related Quality of Life
ITT	Intention to Treat
LHRH	Luteinising Hormone-Releasing Hormone
MedDRA	Medical Dictionary for Regulatory Activities
MRI	Magnetic Resonance Imaging
NCI-CTCAE	National Cancer Institute - Common Terminology Criteria for Adverse Events
OS	Overall Survival
PP	Per Protocol
PSA	Prostate Specific Antigen
PSADT	PSA Doubling Time
CCI	[REDACTED]
RAP	Reporting and Analysis Plan
CCI	[REDACTED]
RP	Radical Prostatectomy
SAE	Serious Adverse Event/Experience
SD	Standard Deviation
SF-36	36-Item Short Form Health Survey
SOP	Standard Operating Procedure
TEAE	Treatment Emergent Adverse Event
CCI	[REDACTED]
US	Ultrasound
WHO	World Health Organisation

1. INFORMATION TAKEN FROM THE PROTOCOL

1.1. Study objectives

1.1.1. *Primary objective*

To assess the benefit of immediate adjuvant chemical castration after radical prostatectomy (RP) in patients with high-risk prostate cancer expressed as biochemical relapse-free survival (BRFS).

1.1.2. *Secondary objectives*

[figure not shown]
To compare the two groups in terms of:

- Event-Free Survival (EFS), Overall Survival (OS), Disease Specific-mortality rate and prostate specific antigen doubling time (PSADT)
- Impact on health-related quality of life (HRQoL)

To assess overall safety of immediate chemical castration.

1.1.3. *Ancillary Exploratory objectives*

CCI

1.2. Study design

This open, prospective, multicentric, multinational, randomised, controlled study with two parallel groups is designed to compare the efficacy and safety of immediate 9-month adjuvant treatment using triptorelin 11.25 mg (treatment onset no later than 8 weeks after RP) versus active surveillance, after RP. Both groups will be monitored at the same frequency of visits (one visit every 3 months). Assessments will be performed to identify any BR/Clinical Disease Progression. This study will be conducted in a Phase IV setting in Russia and China, where triptorelin is approved for the treatment of locally advanced or metastatic prostate cancer.

1.2.1. Study population

The study will be performed in males aged at least 18 years, with histopathologically confirmed adenocarcinoma of the prostate, without positive margins, no pathological positive lymph nodes or metastases and with a high risk of disease progression (Gleason score ≥ 8 on prostatectomy specimen and/or pre-RP PSA level ≥ 20 ng/mL and/or pT3a). Patients must have undergone RP no more than 8 weeks prior to randomisation, with post-RP (6 weeks) PSA levels ≤ 0.2 ng/mL, however no other treatment for prostate cancer was permitted. A total of 226 patients will be included from approximately 10 centres, 113 in each group.

1.2.1.1. Inclusion criteria

Each patient must meet the following criteria:

- Provide written informed consent by the patient prior to any study-related procedure
- Men aged ≥ 18 years
- Histo-pathologically confirmed adenocarcinoma of the prostate
- Radical Prostatectomy with curative intent performed no more than 8 weeks before randomisation
- High-risk criteria of disease progression, defined as follows:
 - Gleason score ≥ 8 on prostatectomy specimen, and/or
 - Pre-RP PSA level ≥ 20 ng/mL, and/or
 - Primary tumour stage 3a (pT3a) (with any PSA and any Gleason score)
- Post-RP PSA levels ≤ 0.2 ng/mL at 6 weeks.
- Eastern cooperative oncology group (ECOG)/world health organisation (WHO) performance status of 0 to 1

1.2.1.2. Exclusion criteria

Patients presenting any of the following criteria were not included in the study:

- Has evidence of lymph nodes or distant metastasis
- Has positive margins
- Has evidence of any other malignant disease, not treated with a curative intent
- Previously received or is currently receiving any treatment of prostatic cancer besides the concerned RP
- Had a surgical castration
- Has a life expectancy of < 5 years
- Suffers from a significant comorbidity or an untreated infection
- Is likely to require treatment during the study with drugs that are not permitted by the study protocol
- Has a history of hypersensitivity to triptorelin or any luteinising hormone releasing hormone (LHRH) analogues or to any of the excipients of triptorelin 11.25 mg
- Was treated with any investigational drug within 4 weeks before the study entry

- Has abnormal baseline findings, any other medical condition(s) or laboratory findings that, in the opinion of the Investigator, might jeopardise the patient's safety or decrease the chance of obtaining satisfactory data needed to achieve the objective(s) of the study
- Is unable to undergo regular follow-up
- Has any mental condition rendering him unable to understand the nature, scope and possible consequences of the study, and/or evidence of an uncooperative attitude
- Has a history of, or known current, problems with alcohol or drug abuse.

1.2.2. Study exposure

The anticipated recruitment period of this study is 2 years.

For each patient, study participation is planned to be at least 36 months. Follow-up may continue beyond this if BR is not reported at 36 months and the statistically required 61 BRs have not yet been reached, in which case the patient will continue on study until one of these events occurs.

The overall duration of study is estimated to be approximately 60 months.

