RAP Final Version 3 [22-JUL-2019]

15/248

CCI

1 Adverse events (AEs) will only be collected until Visit 5/Month 9; this corresponds to three months after the last triptorelin injection for those patients in the triptorelin group. After this visit, only AEs and SAEs related to triptorelin according to Investigator's judgement should be reported (with the exception of AEs resulting in death that should be reported until the end of the study).

Patients will not be withdrawn from the study if study medication is discontinued. Follow-up will continue for all patients every 3 months and for at least 36 months.

1.3.4. *Planned sample size*

It is planned to recruit 226 patients in approximately 10 centres in two countries (China and Russia) according to the Sample Size Determination.

The sample size estimation was based on the primary efficacy endpoint of BRFS. Assuming that with RP alone, the probability of biochemical (PSA) relapse as defined in Section 4.2.1 of the study protocol at 36 months after RP is 40% in high-risk patients (Section 2.1 of the study protocol, Table 1), and anticipating that immediate adjuvant hormonal therapy added to RP will reduce this probability to 20% (percentage considered to be clinically relevant), 113 patients per treatment group (226 in total) are required in order to detect such a difference using a two-sided log-rank test at a significance level of 5% and a power of 90%, assuming a common 1% exponential dropout rate (corresponding to an approximate 5% dropout rate per year).

These 226 patients are required to observe 61 BR in order to achieve 90% power. For patients with no sign of disease progression at 36 months post-randomisation, monitoring will continue until the 61 BR events are observed at the study global level. If the 61 events are observed before all patients complete the 36 months post-randomisation monitoring period, the study will be continued until those patients reach their 36 month visit (Visit 14).

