Event	Decision	Date of event or censor to consider for analysis
Clinical disease progression or death from any cause	Not censored	Date of clinical disease progression or death
No clinical disease progression and no death and no premature withdrawal from the study	Censored	Date of last visit
No clinical disease progression no death and patient premature withdrawal from the study or lost to follow-up	Censored	Date of withdrawal from the study or last contact

- OS

Event	Decision	Date of event or censor to consider for analysis
Death from any cause	Not censored	Date of death
Patient alive and no premature withdrawal from the study	Censored	Date of last visit
Patient premature withdrawal from the study or lost to follow-up	Censored	Date of withdrawal from the study or last contact

- Disease-specific mortality

Event	Decision	Date of event or censor to consider for analysis
Death related to prostate cancer	Not censored	Date of death
Death not related to prostate cancer	Censored	Date of death
Patient alive and no premature withdrawal from the study	Censored	Date of last visit
Patient premature withdrawal from the study or lost to follow-up	Censored	Date of withdrawal from the study or last contact

- PSADT

Event	Decision	Date of event or censor to consider for analysis
First PSA value > than twice that of the first increased value (> 0.2 ng/mL)	Not censored	Date of sample when the first PSA value > than twice that of the first increased value
No PSA value 2 times higher than the first increased value or no increased value and no premature withdrawal from the study	Censored	Date of last evaluable sample
Patient premature withdrawal from the study or lost to follow-up	Censored	Date of last evaluable sample before withdrawal from the study or last contact

Incomplete dates for time-to-event analyses will be handled as follows:

- If the day of the randomisation is missing and month is present, the 15 of the month will be used.
- If the day of the BR, clinical progression or death is missing and month is present, the 01 of the month will be used.
- If the month (or the date) of the death is missing, the date of the last contact will be used.
- The other dates with missing month will be studied case by case.

Castrated patients

A patient will be considered as:

- Castrated if the testosterone level is inferior to 50 ng/dL for the test or confirmation test.

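### After Month 36 only relapse-free patients stay under follow-up, so EFS, OS and disease-specific mortality are informatively censored from then on; the effect is modest at planned relapse rates

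*SAP*

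**What the plan says.** Two places in the SAP govern follow-up after Month 36.

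- **Section 1.2.2 (Study exposure).** Every patient is followed for at least 36 months. He may continue if he has no BR at 36 months and the study has not reached 61 BRs, "in which case the patient will continue on study until one of these events occurs". The two events are his own BR and the 61st BR in the study.
- **Section 1.3.4 (Planned sample size).** "For patients with no sign of disease progression at 36 months post-randomisation, monitoring will continue until the 61 BR events are observed" in the study as a whole. Nothing is said about leaving at one's own BR. Footnote e of Table 1 counts BR as disease progression, so a patient with BR by Month 36 is not extended here either.

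Section 3.2.10 sets the censoring. For OS and disease-specific mortality, the row "Patient alive and no premature withdrawal from the study" is censored at the last visit. EFS has an equivalent row. Sections 3.2.1.2.1 to 3.2.1.2.3 analyse all three endpoints as BRFS is analysed: log-rank, Kaplan-Meier and Cox. There is no Month 36 cut for them and no status collection after study exit. The sensitivity analyses in Section 3.2.1.1 concern BRFS only.

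**The concern.** Log-rank, Kaplan-Meier and Cox analyses assume that a censored patient has the same future risk as a comparable patient still under observation. After Month 36 that fails by design. Who remains depends on BR, which is the trial's own marker of recurrence and plausibly raises the later risk of clinical progression and prostate cancer death. The late risk sets would consist of relapse-free men, while the curves would be labelled as EFS or OS for all randomised patients.

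The selection also differs by arm, because treatment is expected to change BR: more surveillance than triptorelin patients are removed. At stake are the part of the secondary curves beyond Month 36 and, to a lesser degree, hazard ratios that use that follow-up.

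**Working it through.** **1. Reproduce the plan's event count.** Inputs from Section 1.3.4: BR probability "at 36 months after RP is 40% in high-risk patients", treatment "will reduce this probability to 20"%, two-sided 5% level, 90% power. With exponential BR times, HR = ln 0.8 / ln 0.6 = 0.437. Schoenfeld: 4 × (1.960 + 1.282)² / (ln 0.437)² = 61.27. With 61 events the power is 89.9%. The plan's 61 is reproduced.

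**2. Is the extension expected?** Monthly BR hazards are −ln 0.6 / 36 = 0.01419 and −ln 0.8 / 36 = 0.00620. Recruitment takes 24 months (Section 1.2.2) and is assumed uniform.
- *No dropout, 44 months after first randomisation.* Follow-up runs from 20 to 44 months. The expected BR proportions are 0.362 and 0.179, so 113 × 0.541 ≈ 61 BRs.
- *Dropout of 5% per year.* Section 1.3.4 gives both 1% exponential and about 5% per year; the latter is used. At 46.5 months the expected observed proportions are 0.359 and 0.178, or about 60.7 BRs. The 61st BR falls at about month 46 to 47.

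So the extension is expected on the plan's own inputs.

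**3. Who stays and who is removed?**
- *No dropout.* (44 − 36)/24 = 33% of patients reach Month 36 before the 61st BR. Those who stay are 0.333 × 0.6 = 20% of surveillance and 0.333 × 0.8 = 27% of triptorelin.
- *With dropout.* (46.5 − 36)/24 × 0.95³ = 0.375. Those who stay are 0.375 × 0.6 = 22.5% and 0.375 × 0.8 = 30%. Those stopped at Month 36 because of an earlier BR are 0.375 × 0.4 = 15% and 0.375 × 0.2 = 7.5%.

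Simulation agrees: about 20–23% and 26–31% have follow-up past Month 36. Under Section 1.2.2 a further 1.6% and 1.0% leave at a later BR.

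**4. Size of the bias at plan rates.** Large simulated samples, 5% per year dropout. The event hazards before and after BR are assumptions, because the SAP gives none. Event-free percentage at month 47 under a common cut-off for all / the 1.2.2 rule / the 1.3.4 wording:

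| Hazard per month before / after BR | Surveillance | Triptorelin | HR, common cut-off → 1.2.2 |
|---|---|---|---|
| 0.0005 / 0.002 | 95.87 / 96.47 / 96.40 | 96.73 / 97.14 / 97.04 | 0.793 → 0.800 |
| 0.001 / 0.005 | 91.12 / 92.55 / 92.17 | 93.38 / 94.05 / 93.91 | 0.777 → 0.787 |
| 0.001 / 0.01 | 86.30 / 89.58 / 89.01 | 91.03 / 92.60 / 92.34 | 0.661 → 0.672 |

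In the last row surveillance is overstated by 3.28 points and triptorelin by 1.57. The gap between arms shrinks from 91.03 − 86.30 = 4.73 to 92.60 − 89.58 = 3.02 points. Estimates at Month 36 are identical under all three rules. With equal hazards before and after BR the bias vanishes apart from simulation noise.

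These are late points on the curve. With 113 per arm and no dropout, only about 6 surveillance and 8 triptorelin patients are still at risk at month 43. In events, with 1% to 3% per month after BR, the rule loses roughly 0.5 to 2 surveillance EFS events out of about 10 to 21; at lower post-BR hazards it loses fewer.

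**5. If BR is slower than planned.** At 80% of plan hazards the 61st BR falls at about month 56, 24% and 12% are stopped at Month 36 because of BR, and the HR moves from 0.770 to 0.811 (hazards 0.001 / 0.005). At 60% it moves from 0.769 to 0.850. At 75%, about 2 to 6 surveillance EFS events are lost with 1% to 3% per month after BR.

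**The case against.** The best case against the point is about size.

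- **Few patients and few events lie beyond Month 36.** At plan rates the hazard ratio barely moves, and percentage-point biases late in the curve are read where a handful of men remain. This stands, and it is why the effect is called modest.
- **The post-BR hazards are invented.** Section 1.3.1 bars other therapy in the surveillance group only before clinical or biochemical progression, so relapsed patients may be treated and their risk is uncertain. This stands: direction and range are supported, a single figure is not.
- **Section 1.3.4 does not say that patients leave at their own BR.** True, so it cannot be taken as settled that every later relapser leaves. But patients with BR by Month 36 are dropped under both wordings, so the bias becomes smaller without disappearing.
- **The notes to Table 1 promise follow-up for all patients for at least 36 months.** That sets a floor. It protects estimates up to Month 36 and nothing later.
- **The exit rule is protocol information.** It is, and the protocol is not at hand. The censoring rules in Section 3.2.10 belong to the SAP and can be changed there.
- **Few deaths are likely**, given the exclusion of life expectancy under 5 years. This is fair. The mechanism applies to OS and disease-specific mortality, but no figure is offered for them.

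A reader might also infer that a third of patients have follow-up past Month 36. One third is the share whose Month 36 falls before the 61st BR without dropout; those with BR by then leave, so the share followed further is smaller.

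**Conclusion.** The point holds in limited form. Sections 1.2.2 and 1.3.4 disagree on whether a BR after Month 36 ends follow-up. Under either, censoring of EFS, OS and disease-specific mortality after Month 36 depends on BR, and nothing in the SAP corrects for it. If BR raises later risk, the late curves are too high in both arms, more so in surveillance.

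A reader might infer that the benefit of triptorelin is overstated. The documents do not support that. More relapsed patients are removed from surveillance, so the hazard ratio is pulled toward 1. Nor is the primary analysis touched: BR is itself the BRFS event, so leaving at or after BR removes no BRFS information.

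The size is modest at plan rates and grows if BR is slower than planned. These sizes rest on exponential BR times, uniform accrual and assumed pre- and post-BR hazards. The point deserves a correction because the remedy is cheap, not because the expected distortion is large.

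**What to change.** In Section 3.2.10, add one rule for EFS, OS and disease-specific mortality: in the main analysis every patient without an event by Month 36 is censored no later than Month 36, whatever his BR status, and later events are not counted. Define the cut as a fixed time from randomisation, for example 36.0 months on the SAP's own scale. Show follow-up beyond Month 36 descriptively, with numbers at risk and a note that only relapse-free patients were extended. The cost is SAP wording and the loss of a few late events.

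Reconcile Sections 1.2.2 and 1.3.4 on whether a BR after Month 36 ends follow-up.

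If late EFS and survival matter to the sponsor, the alternative is to collect progression and survival status for all patients to a common cut-off regardless of BR. That needs extra status contacts and is a matter for the protocol.

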1.3. Methods and procedures

1.3.1. Patient identification and allocation to study treatment

All patients enrolled must be identifiable throughout the study. At Screening, potential patients will be allocated a patient number. Patients will be enrolled sequentially and assigned the lowest identification number available.

After eligibility is confirmed, patients will be assigned a randomisation number and will be randomised in one of two treatment arms ("Triptorelin treatment" or "Active surveillance") in accordance with the randomisation procedure.

For patients randomised to the triptorelin treatment group, triptorelin 11.25 mg will be administered intramuscularly every 3 months (± 7 days), for a total of three injections (at the Baseline, 3 and 6 months visits). For patients randomised to the active surveillance group, no adjuvant treatment with any method (hormonal or surgical castration and/or radiation therapy) should be initiated prior to evidence of disease progression (clinical or biochemical).

1.3.2. Patients assessments

Methods for derivation of calculated variables are detailed in Section 3.2.10.

1.3.2.1. Efficacy assessments

PSA

Blood samples for PSA testing will be taken every 3 months (except at Visit 2 (Baseline, Day 1 Month 0) where PSA level is not required).

Biochemical Relapse

Biochemical Relapse definition: increased PSA >0.2 ng/mL confirmed by a second measurement performed 4 to 6 weeks later. The time-point at which the first elevated PSA measurement is >0.2 ng/mL is recorded will be deemed to be the time of BR.

To note, for the identification of BR; all PSA samples will be taken into account, even if several samples are within the same time windows.

Clinical disease progression

Clinical disease progression is defined as evidence of local/locoregional recurrence and/or lymph node involvement and/or distant metastases documented by relevant standard investigations (such as ultrasound (US) guided biopsy, X-ray, computed tomography (CT) scan, or magnetic resonance imaging (MRI) guided biopsy).

Survival status

Survival status will be recorded at each visit.

Serum Testosterone

Serum testosterone in the triptorelin treatment group will be recorded at baseline, 3, 6 and 9 months. It will be assessed both as a continuous and as a qualitative variable (< 50 ng/dL / ≥ 50 ng/dL).

Health-Related Quality of Life

Health-Related Quality of Life (HRQoL) will be assessed using the FACT-P questionnaire, version 4, and the 36-item short form (SF-36) health survey, version 2 in both treatment arms at Baseline, 9, 24, and 36 months..

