1.3.3. Schedule of assessments

Table 1. Schedule of Assessments

Visit	1	2	3	4	5	6	7	8	9	10	11	12	13	14	XX
	Screening	Baseline	3M	6M	9M	12M	15M	18M	21M	24M	27M	30M	33M	36M	Every 3M
Informed Consent	X														
Demographic Data	X														
Medical History	X														
Eligibility Criteria	X	X													
Physical Examination	X	X	X	X	X	X	X	X	X	X	X	X	X	X	X
Vital Signs		X													
ECOG/WHO Performance Status		X			X					X				X	
Randomisation		X													
Testosterone Level [a], [b]		X	X [c]	X [d]	X [d]										
Blood Chemistry and Haematology	X				X										
PSA Level [e]	X		X	X	X	X	X	X	X	X	X	X	X	X	X
Clinical Disease Progression Assessment [f]			X	X	X	X	X	X	X	X	X	X	X	X	X

CCI

CONFIDENTIAL

RAP Final Version 3 [22-JUL-2019]

14/248

Visit	1	2	3	4	5	6	7	8	9	10	11	12	13	14	XX
FACT-P Questionnaire		X			X					X				X	
SF-36 Health Survey		X			X					X				X	
Triptorelin Injection [a]		X	X	X											
Prior and Concomitant Medication/Therapy	X	X	X	X	X	X	X	X	X	X	X	X	X	X	X
Prior and Concomitant Non-Drug Therapy	X	X	X	X	X	X	X	X	X	X	X	X	X	X	X
AEs [1]	X	X	X	X	X	X [1]									
Visit Status	X	X	X	X	X	X	X	X	X	X	X	X	X	X	X

AE, adverse event; CCI, prostate specific antigen; ECOG, Eastern Cooperative Oncology Group; FACT P, functional assessment of cancer therapy prostate; M, month; PSA,

CC1

- a Only for the triptorelin adjuvant treatment group (± 7 days)
- b Always prior to each triptorelin injection (Baseline, 3 months, and 6 months)
- c Evidence of lack of castration at 3 months/Visit 3 will be documented by serum testosterone ≥50 ng/dL (≥0.50 ng/mL) confirmed by a second elevated serum testosterone level at least two weeks later. For the other testosterone assessment time points (Baseline, and 6 and 9 months), no confirmation test is required.
- d If evidence of lack of castration at 3 months/Visit 3, therefore testosterone sampling is not required anymore at Visit 4/Month 6 and Visit 5/Month 9.
- e Starting from Visit 3, any elevated PSA concentration >0.2 ng/mL should be confirmed by a second measurement performed 4 to 6 weeks later. No confirmation test is required after evidence of disease progression (biochemical relapse (BR) and/or clinical disease progression).
- f Clinical disease progression assessments (such as ultrasound [US] guided-biopsy, X-ray, computed tomography [CT] scan, magnetic resonance imaging [MRI]) can be performed at any time during the study at the Investigator's discretion and as per local standard care.

CC1

CONFIDENTIAL

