No BR and no clinical disease progression and new hormonal treatment (ie triptorelin or similar)	Censored	Date of last evaluable sample before the start of new hormonal treatment
No BR and no clinical disease progression and no premature withdrawal from the study	Censored	Date of last evaluable sample assessment
No BR and no clinical disease progression and patient premature withdrawal from the study or lost to follow-up	Censored	Date of last evaluable sample before withdrawal from the study or last contact
Clinical disease progression before BR	Censored	Date of clinical disease progression
No BR but death	Censored	Date of last evaluable sample assessment

- BRFS – Sensitivity Analysis 1

Event	Decision	Date of event or censor to consider for analysis
BR	Not censored	Date of BR (i.e. date of the first elevated PSA measurement is >0.2 ng/mL*)
At least two consecutive visits missing before BR	Censored	Date of last visit preceding the missing consecutive visits
No BR and no clinical disease progression and new hormonal treatment (ie triptorelin or similar)	Censored	Date of last evaluable sample before the start of new hormonal treatment
No BR and no clinical disease progression and no premature withdrawal from the study	Censored	Date of last evaluable sample assessment
No BR and no clinical disease progression and patient premature withdrawal from the study or lost to follow-up	Censored	Date of last evaluable sample before withdrawal from the study or last contact
Clinical disease progression before BR	Censored	Date of clinical disease progression
No BR but death	Censored	Date of last evaluable sample assessment

- BRFS – Sensitivity 2

Event	Decision	Date of event or censor to consider for analysis
BR	Not censored	Date of BR (i.e. date of the first elevated PSA measurement is >0.2 ng/mL*)
Death (whatever the reason) without BR	Not censored	Date of death
No BR and no clinical disease progression and new hormonal treatment (ie triptorelin or similar)	Censored	Date of last evaluable sample before the start of new hormonal treatment
No BR and no clinical disease progression and no premature withdrawal from the study	Censored	Date of last evaluable sample assessment
No BR and no clinical disease progression and patient premature withdrawal from the study or lost to follow-up	Censored	Date of last evaluable sample before withdrawal from the study or last contact
Clinical disease progression before BR	Censored	Date of clinical disease progression

- EFS

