3.2.11. Visit windows

All data will be organised and analysed according to the scheduled visits outlined in the protocol. However, actual observation times may differ from the scheduled visit times and where this occurs the results should be allocated to the most appropriate visit. Therefore, time intervals (e.g. visit windows) have been constructed so that every observation collected after baseline visit can be allocated to a particular time point. If more than one record occurs within the same visit window where only one assessment is expected then the following rule should be applied (except for PSA and testosterone sample): for pre-study assessments only one record is expected and corresponds to the baseline visit; for post-treatment assessments the closest non-missing result to the scheduled visit should be used.

Scheduled visit	Time interval (days)
Baseline [V2]	1
Month 3 [V3]	2 to 138
Month 6 [V4]	139 to 229
Month 9 [V5] ^(a)	230 to 321
Month 12 [V6]	322 to 412
Month 15 [V7]	413 to 503
Month 18 [V8]	504 to 595
Month 21 [V9]	596 to 686
Month 24 [V10] ^(a)	687 to 777
Month 27 [V11]	778 to 868
Month 30 [V12]	869 to 960
Month 33 [V13]	961 to 1051
Month 36 [V14] ^(a)	1052 to 1142
X visit post Month 36 - Every 3 months	$((36+3*X-1.5)*30.4375+2)$ to $((36+3*X+1.5)*30.4375+1)$
Time interval (days): Date of visit – Date of baseline visit +1	
(a) sHRQoL assessment	

3.2.12. *Window for assessment for the PSA and testosterone parameters*

Testosterone (only in the triptorelin treatment group) should be assessed at 3; 6 and 9 months (± 14 days). At visit 3, evidence of lack of castration will be confirmed by a second test at least 2 weeks later.

PSA should be assessed every 3 month (± 14 days) except at Visit 2 (Baseline, Day 1 Month 0). Elevated PSA concentration (>0.2 ng/mL) must be confirmed by a second test 4 to 6 weeks later (acceptable delta of 14 days).

Scheduled visit	Time interval (days) for serum testosterone assessment		Time interval (days) for PSA Level assessment	
	As per protocol (± 14 days)	Used for analysis (Consecutive intervals)	As per protocol (± 14 days)	Used for analysis (Consecutive intervals)
Month 3 [V3] ^(a,b)	78 to 106	2 to 138	78 to 106	2 to 138
Month 6 [V4] ^(a,b)	170 to 198	139 to 229	170 to 198	139 to 229
Month 9 [V5] ^(a,b)	261 to 289	230 to 321	261 to 289	230 to 321
Month 12 [V6] ^(b)	--	--	352 to 380	322 to 412
Month 15 [V7] ^(b)	--	--	444 to 472	413 to 503
Month 18 [V8] ^(b)	--	--	535 to 563	504 to 595

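### The SAP gives two confirmation windows for biochemical relapse and does not say how a PSA that stays above 0.2 ng/mL without an in-window retest is classified; read literally, it is censored

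*SAP*

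**What the plan says.** Three places in the SAP set the confirmation rule.

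- Section 1.3.2.1 defines BR as "increased PSA >0.2 ng/mL confirmed by a second measurement performed 4 to 6 weeks later" and dates it at the first elevated sample. It adds that "all PSA samples will be taken into account, even if several samples are within the same time windows" when BR is identified.
- Section 1.3.3, note e, applies from Visit 3: "any elevated PSA concentration >0.2 ng/mL should be confirmed by a second measurement performed 4 to 6 weeks later". No tolerance is given.
- Section 3.2.12 says an elevated value "must be confirmed by a second test 4 to 6 weeks later (acceptable delta of 14 days".

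On the schedule, 3.2.12 states "PSA should be assessed every 3 month (± 14 days" and tabulates the per-protocol windows.

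The BRFS table in 3.2.10 has one row for BR, counted as an event. The other rows are for patients without BR or with clinical progression first, and all of them censor. One row reads "No BR and no clinical disease progression and no premature withdrawal from the study" and censors at the last evaluable sample. The row for men without BR who start new hormonal treatment censors at "Date of last evaluable sample before the start of new hormonal treatment". No row covers an elevated PSA that was not retested, or one followed by another elevated value only outside the window.

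**The concern.** BR is the primary event, and 61 BRs trigger the primary analysis. If the confirmation interval is part of the definition, BR requires a sample beyond the 3-monthly schedule, taken within a set number of days. A man with, say, 0.4, 0.9 and 2.0 ng/mL at Months 12, 15 and 18 and no usable retest has plainly sustained elevation. On the literal text he counts as relapse-free up to his last sample.

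The two windows also disagree on individual retests. One at day 50 confirms under 3.2.12 but not under 1.3.2.1 or note e. So does one at day 20, if the tolerance applies on both sides. Two programmers could derive different event counts from the same data.

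The trial is open-label, so retest timing could differ between arms. The SAP has no analysis that would show whether it did.

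**Working it through.** **1. The plan's own event figure (1.3.4).** Inputs: 36-month BR probability 40% with surgery alone and 20% with triptorelin, two-sided 5%, 90% power, 1:1 allocation.

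- HR = ln(0.80)/ln(0.60) = 0.437.
- Schoenfeld events = 4 × (1.960 + 1.282)² / (ln 0.437)² = 61.3, against 61 stated. Power at 61 events is 0.899. The figure reproduces.

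**2. Can scheduled samples confirm each other?** Per-protocol PSA windows (3.2.12): days 78–106, 170–198, 261–289, and so on to 1083–1111.

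- Shortest gap between consecutive windows: 261 − 198 = 63 days (others are 63 or 64).
- Confirmation interval in 1.3.2.1 and note e: 28 to 42 days.
- With the tolerance in 3.2.12: at most 42 + 14 = 56 days (and from 28 − 14 = 14 days if it applies on both sides).
- 63 > 56 > 42, so two on-schedule samples never confirm each other.

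**3. Who is actually missed?** Each elevated value calls for its own retest, and all samples count, so one skipped retest is not enough. A late retest may also pair with the next visit. At 91-day spacing (3 × 30.4375):

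- With 14 to 56 days allowed, a retest at day 57 to 77 falls 34 to 14 days before the next visit, and that pair confirms.
- With 28 to 42 days allowed, a retest at day 49 to 63 falls 42 to 28 days before the next visit, and that pair confirms.

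The gap is men with no usable pair at any elevated visit.

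**4. Do other analyses catch them?** The three BRFS sensitivity analyses in 3.2.1.1 concern two consecutive missed visits, death as an event, and exclusion of men lost to follow-up. A man who attends every visit without a usable retest is untouched by all three. PSADT (3.1.2, 3.2.10) starts at the first value above 0.2 ng/mL and states no confirmation. In the example, 0.9 exceeds 2 × 0.4 = 0.8, so he has a PSADT event at Month 15 while censored for BRFS.

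**5. Expected BRs by each patient's Month 36.** Exponential hazards and 5% dropout per year (1.3.4):

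- Monthly hazards: −ln(0.60)/36 = 0.01419 and −ln(0.80)/36 = 0.00620; dropout −ln(0.95)/12 = 0.00427.
- P(BR observed) = λ/(λ+δ) × (1 − e^(−36(λ+δ))) = 0.373 and 0.186.
- Expected BRs = 113 × (0.373 + 0.186) = 63.2. Without dropout: 113 × 0.60 = 67.8.

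**6. Illustration of loss.** The share m of relapses without a usable pair is not in the SAP; the values are assumptions.

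| m, equal in both arms | BRs counted by Month 36 (63.2 × (1 − m)) | True relapses needed for 61 counted (61/(1 − m)) |
|---|---|---|
| 5% | 60.0 | 64.2 |
| 10% | 56.9 | 67.8 |
| 20% | 50.6 | 76.2 |

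- m = 10% in both arms: ln(0.82)/ln(0.64) = 0.445, almost unchanged from 0.437.
- m = 10% in surveillance only: ln(0.80)/ln(0.64) = 0.50.
- m = 10% in triptorelin only: ln(0.82)/ln(0.60) = 0.39.

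**The case against.** The strongest reply is that the SAP does not state that such a man is censored. The note in 1.3.2.1 that all PSA samples count could be meant to let a later elevated visit value confirm. The BR row in 3.2.10 carries an asterisk whose note is not visible in the text available, and Section 5 breaks off just as it introduces changed rules for several PSA samples in one window. The missing text may bear on the question. This stands as a limit: censoring is the literal reading of a table with a gap, not a written rule. It does not remove the gap. The note's own qualifier concerns several samples in one window, and it says nothing about the confirmation interval.

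A reader might infer that any skipped or late retest loses the relapse. Note e and the inclusion of all samples rule that out.

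A reader might also infer that power is lost. Sections 1.2.2 and 1.3.4 continue follow-up until 61 BRs, so an equal loss costs time. Nor should the margin over 61 be taken from 67.8, which ignores the planned dropout.

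Finally, a one-arm loss is pure assumption: both arms have the same visit frequency (1.2), and nothing in the SAP indicates a direction.

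**Conclusion.** The point holds in a limited form. The SAP gives two confirmation windows, on-schedule samples cannot confirm each other under either, and persistent elevation without an in-window pair has no classification rule. The literal result is censoring in the primary analysis, untested by any sensitivity analysis.

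The size cannot be derived from the SAP. With about 63 BRs expected by Month 36 against 61 needed, even a 5% equal loss could push the trigger past Month 36, but the estimate would barely move. Appreciable bias requires unequal loss; the range 0.39 to 0.50 around 0.437 shows what an assumed 10% loss in one arm would do and is not a prediction. These figures rest on exponential hazards, the planning rates and 5% dropout per year.

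A reader might conclude that the primary definition must be replaced by one with no upper time limit. The document does not support that. Section 1 is taken from the protocol, 1.3.4 places the relapse definition in protocol section 4.2.1, which is not shown, and such a rule could pair samples far apart with missed visits between them.

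**What to change.** - State one confirmation tolerance in 1.3.2.1, 1.3.3 note e and 3.2.12, consistent with the protocol definition, and say whether it applies on both sides.
- In the BRFS rules of 3.2.10, state how a PSA above 0.2 ng/mL is classified when it has no in-window retest but the next available PSA is also above 0.2 ng/mL.
- Report the number of such men by arm.
- Add a BRFS sensitivity analysis that counts them as BR at the first elevated sample. If the protocol definition already allows them as BR in the main analysis, run the strict window as the sensitivity analysis instead.

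The cost is some SAP wording, one derived flag and one more analysis, all from PSA data already collected. The downside is that some BRs in the relaxed analysis are confirmed later than the stated window. The rule also does not resolve a man with a single elevated value who starts hormonal treatment before any retest and whose next PSA is suppressed; he would remain censored.
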